8.5. Study Population

The study population comprises 25 adult patients aged between 40 and 65 years, enrolled consecutively, under the care of the Rizzoli Orthopaedic Institute, who are undergoing opening wedge HTO for the treatment of medial compartment OA of the knee. The study team believe the research burden on study participants is moderate with one pre-operative visit required and 5 visits required for post-operative follow-up after 1, 3, 6, 12 and 24 months. The team are confident that study dropout rates will be relatively low, and will also utilise letter, e-mail and SMS communications to encourage patient attendance at all follow up time frames. As such, it has been advised that this population number is sufficient to meet the pilot study aims.

8.6. Identifying potential study participants

Patients will be identified as potential participants in one of two ways. Firstly, by their surgeon when they are initially listed for opening wedge HTO surgery at their out-patient consultation at the Rizzoli Orthopaedic Institute. The surgeon will outline the study, provide the patient with the study consent form containing information about the study (Appendix 3) and ask permission to the patient to allow one of the research team to contact them to discuss the study further. Alternatively, potential participants will be identified from the current surgical waiting list as suitable for inclusion by a member of the direct care team. In this latter case, one of the direct care team will telephone the patient requesting permission for one of the research team to contact them by telephone to discuss the study and to enquire if the patient would be interested in participating in the study. Information about the study will be sent to potential participants in advance of the research team contacting them. The number of patients approached and invited to take part in the study will be recorded.

The patient will have an opportunity to further discuss the research project as well as provisionally agree or decline enrolment during this telephone call.

The Rizzoli Orthopaedic Institute carry out approximately 200 HTO procedures per year. We understand that studies have, on average, a low percentage of potential participants who choose not to be part of the research. Consequently, we believe it is reasonable to recruit about 10 cases per month (i.e. 60% participation rate). However, we will allow for 6 months to achieve our sample size of 25 in case recruitment is slower than anticipated.

8.7. Study settings

The study will be conducted in the 2nd Orthopaedic and Traumatology Clinic at the Rizzoli Orthopaedic Institute in Bologna, which is an IRCCS hospital, and hence places particular importance on research assignments. This centre is also the orthopaedic clinic for the Faculty of Medicine at the University of Bologna. The procedure with the novel device under investigation will be performed at the Rizzoli, thus the data will also be collected there, more specifically in the Movement Analysis Laboratory and Functional - Clinical Evaluation of Prostheses. However, the specific data collected pre and post intervention will be sent to the company manufacturing the device under investigation (3D Metal Printing) in the UK.

To be able to identify all the investigation centres involved in the study, page 1 and 2 have been inserted to provide essential information relating to the investigation.

8.8. Study flow and timeline

Study flow is outlined and summarised in Appendix 11.

8.9. Pre-operative radiological & functional assessment

The 25 patients enrolled in this study investigating the medical device (TOKA®) will undergo a pre-operative CT scan of the affected leg, which will be through the hip, knee and ankle. The CT scan will be conducted according to hospital routine protocol. Other pre-operative scans needed are AP, lateral 30°, merchant view and hip and lower limb panoramic frontal load bearing X-rays (also conducted according to hospital routine protocol).

These images are then used to perform a pre-operative plan, by the surgeon and the support staff, to enable the creation of the custom-made TOKA® components. The procedure for determining the key variables (Mikulicz point, hinge point, correction angle and opening distance) is done following a modification of Miniaci's Method for opening wedge osteotomy cases, which is the process used in the Rizzoli Orthopaedic Institute for routine opening wedge HTO cases. This method consists in 6 main steps:

1. The tibial plateau width is measured just below the joint line. Subsequently, a line is drawn from the centre of the femoral head to the centre of the talar dome, which represents the pre-operative weight-bearing or Mikulicz line. This line intersects the tibial plateau at a point termed the Mikulicz point and is typically recorded as a percentage of the tibial width from the medial to the lateral region.
2. Fujisawa's point is then marked and is typically just lateral to the lateral tibial eminence (usually around 62.5% of the tibial width from medial to lateral). Another line is drawn from the centre of the femoral head through the marked Fujisawa's point. This line is extended to indicate the post-operative ankle centre.
3. The hinge point is then identified by extending a line perpendicularly from below the subchondral sclerosis of the lateral tibial plateau till approximately 18mm in males and 15mm in females.
4. Following this step, two lines are drawn – one from the hinge point to the pre-operative ankle centre and another from the hinge point to the post-operative ankle centre. The angle between these two newly marked lines is termed the correction angle and an example can be seen in the figure below.

[figure not shown]

Figure 2: (1) Mikulicz line; (2) Line from centre of femoral head through Fujisawa's point and up to extrapolated post-operative ankle centre; (3) Line from the hinge point to the pre-operative ankle centre; (4) Line from the hinge point to the post-operative ankle centre

5. The obliquity of the osteotomy plane (located above the pes anserinus and projects towards the fibula head) from the vertical line drawn in step 3 is annotated (usually approximately 110°). The proximal osteotomy cut is then projected at this angle.

[figure not shown]

Figure 3:Proximal osteotomy cut at 110° angle

6. Finally, the projected proximal osteotomy cut is moved distally by the previously calculated correction angle to obtain a planned opening. The distance between the proximal osteotomy cut and this distally moved line is the opening distance (Elson).

After the annotation of all these points, lines and angles, the surgeon or investigation team refers them to the TOKA® design team and precision custom-made osteotomy components are generated via modelling software.

Aside from the pre-operative diagnostic images, all study participants will also need pre-operative functional assessments. This will mainly consist in a gait analysis for each patient, which will allow measurement of the location of the loading of the knee joint during functional activity. The analysis will take place at the Movement Analysis Laboratory and Functional-Clinical Evaluation of Prostheses within the Rizzoli Orthopaedic Institute and will be performed by members of the clinical investigation team. The measurements will only take between 10 to 30 minutes. In addition, clinical scores will be registered.

All the pre-operative data needed for each patient undergoing opening wedge HTO with the TOKA® product can be summarised in the table below.

	X-Ray (AP)	X-Ray (lateral 30°)	X-Ray (merchant view)	Hip and Lower Limb Panoramic (frontal load bearing)	CT	GAIT	Clinical scores (KOOS, EQ-5D, Tegner, KSS, VAS)
Pre-operative data	✓	✓	✓	✓	✓	✓	✓

8.10. Admission to hospital for surgery and hospital stay

The admission into the hospital will occur using the routine procedures that the Rizzoli has already put in place and comply with for every HTO case they encounter.

8.11. Surgical procedure

The surgical procedure is one of the most crucial aspects. Surgeon training is given through a video supplied with the TOKA® product, as well as the written instructions in the user manual. A copy of the User Manual and procedure steps can be found in Appendices 12 and 13 respectively. Note that prior to performing the opening wedge HTO surgery, the sterilisation of all the components needs to be performed by using the validated instructions supplied in Appendix 2.

8.12. Post-operative follow-up

For this specific study, participants will be reviewed at 1, 3, 6, 12 and 24 months post-operatively. The table created below shows the post-operative material required for each patient follow-up.

Post-operative follow-up (months)	X-Ray (AP)	X-Ray (lateral 30°)	X-Ray (merchant view)	Hip and Lower Limb Panoramic (frontal load bearing)	CT	GAIT	Clinical scores (KOOS, EQ-5D, Tegner, KSS, VAS)
1	✓	✓					✓
3	✓	✓					✓
6		✓	✓	✓	✓	✓	✓
12	✓	✓					✓
24		✓	✓	✓			✓

As can be seen, the study will terminate at 24 months, after which patients may return to the usual post-operative management schedule (if any is needed).

8.13. Radiation Risk Assessment

Below is a table of the routine and study medical imaging required, which can be used to produce a radiation risk assessment:

Procedure	Pre-Op	Post-Op	Follow-up [month]	No.	Additional Procedure dose	Routine care No.
X-ray (AP)	✓	✓	1, 3, 12	4	≈ 4µSv	4
X-ray (Lateral 30°)	✓	✓	1, 3, 6, 12, 24	6	≈ 4µSv	5
X-ray (Merchant view)	✓	✓	6, 24	3	≈ 4µSv	2
Hip and Lower Limb Panoramic (frontal load bearing)	✓	✓	6, 24	3	≈ 4µSv	2
CT	✓	✓	6	2	≈ 12.6µSv	1

Participants will generally be aged between 40 and 65 years of age. The younger patients will have slightly higher risks, given that they are more sensitive to radiation and they have a longer lifetime for the development of radiation effects (ionising radiation can cause cancer, which manifests itself after many years or decades). Moreover, a category of individuals that could be greatly affected from radiation risks are pregnant women, who are inserted in the exclusion criteria information and so are excluded from the investigation.

For routine clinical care of opening wedge HTO treatment, 14 radiological tests are usually done compared to the 18 planned as part of this investigation. Essentially, in routine clinical care, the 24-month follow-up tests, as well as the standard CT performed at the 6-month follow-up (note that this may be performed sometimes for further evaluations), are not performed.

In the table above, it can be seen that approximately 12µSv is the radiation dose associated with the additional x-rays as part of the study, whereas approximately 12.6µSv is the radiation dose for the extra CT scan performed. These values add to a total of 24.6µSv. If we take into consideration that the average annual radiation dose in the UK is equivalent to 2.7mSv, then 1µSv is comparable to slightly over 2 hours of natural UK background radiation. Another method of comparison to get a better understanding of the figures could be represented by radiation doses during flights. It is estimated that a transatlantic flight (around 6 hours) leads to about 0.08 mSv, and therefore, 1µSv is comparable to about 4.5min on a plane (Public Health England).

This signifies that the figures of additional radiation exposure relating to this study can be compared to about one day of natural UK background radiation or slightly under 2 hours of a transatlantic flight.

With participants' consent, we will use the anonymised data for research on the personalised device, allowing minor optimisations of plate design and surgical technique.

Although there are some additional radiation risks associated with the alternative routine, it can be concluded that this added diagnostic imaging only adds a low extra dosage. These additional examinations are also likely to be extremely beneficial for the assessment of the performance of the device, and so the evaluation of the overall radiation risk is acceptable.

Aside from the risk posed by the radiation, there are also aspects relating to risks of the procedure and device. TOKA® is designed using a risk-based approach, which places great importance on the safety of the patient. Several methods used for assessing the risks are virtual modelling and simulations, along with animal and cadaver tests. Moreover, the design and development of TOKA® follows ISO 14971 to allow conformance to

international risk management standards. The latest risk management table and report can be viewed in Appendices 14 and 15 respectively.

8.14. Interruption of study and patient withdrawal

Following an interruption of the study for any reason, a standard operation procedure must be put in place and enforced to ensure an organised and adequate end to the investigation in order to manage/finalise patient treatment.

All individuals who have not yet been treated with the medical device, but have either:

- Signed written consent,
- or have verbally agreed to enrol in the study, via direct consultation with the surgeon or via telephone call with an investigation team member,

need to be informed promptly that the investigation has been interrupted, and so they will be treated using the routine procedure for opening wedge HTO provided in the specific centre where the study is taking place.

Alternatively, for the individuals who have been treated with the medical device, and that consequently needed to attend follow-up meetings, a new post-operative schedule is used consisting in Rizzoli Orthopaedic Institute routine procedures, shortening the timeline to 12 months instead of 24 months. The table created below shows the routine post-operative material required for each patient follow-up in the event of an interruption of the study.

Post-operative follow-up (months)	X-Ray (AP)	X-Ray (lateral 30°)	X-Ray (merchant view)	Hip and Lower Limb Panoramic (frontal load bearing)	CT	GAIT	Clinical scores (KOOS, EQ-5D, Tegner, KSS, VAS)
1	✓	✓					✓
3	✓	✓					✓
6		✓	✓	✓			✓
12	✓	✓					✓

If the patient should notice any signs of adverse event following the follow-up period of 12 months, then he/she should immediately contact the investigation team for a consultation.

Conversely, if the patient were to withdraw from the study at any point after the surgery, then the data may still be used. As a result, a higher number of patients is recruited to take into account dropout rate, given that if there is a withdrawal before the 24-month follow-up, then this will considerably impact the study timeline (may result in up to a 2-year delay). Therefore, to ensure a minimum of 20 patients are investigated, then 25 are enrolled, which should suffice given the current Rizzoli Orthopaedic Institute dropout rate of up to approximately 13%.

More information on the suspension or early interruption of the study can be found in Chapter 13.

7. Data collection

The knee unit research coordinator or the research nurses employed by the Rizzoli Orthopaedic Institute will collect the pre-operative consent, the pre and post-operative clinical scores. All patients will be given a unique

number for identification and the date of collection will be recorded. Data will be entered onto the study database and the accuracy of the entry will be double checked again by other research coordinators or nurses.

Furthermore, the gait analysis data will be collected at the Movement Analysis Laboratory and Functional-Clinical Evaluation of Prostheses within the Rizzoli Orthopaedic Institute and referenced again by that unique patient identification number and date of collection.

Each surgeon involved will be responsible for clinic data and communications, operation note details, reporting on X-ray finding, which will need to be sent to the sponsor (3D Metal Printing) for component generation.

All other data will be stored on Rizzoli secure computers and it will typically be entered into an Excel spreadsheet.

Clinical scores in use will be as follows:

- Knee Osteoarthritis Outcome score (KOOS)
- The EQ-5D score
- The Tegner score
- The International Knee Society System score (KSS)
- Pain measurements by Visual Analogue Scale (VAS) during rest and activity.

All the data collected will be inserted into the patient's Case Report Form (CRF), of which the template can be seen in Appendix 16. Aside from the clinical scoring, it will contain the following pre-operative and post-operative information: correction angle, HKA angle, Mikulicz point (recorded as a percentage of the tibial width from the medial to the lateral region) and posterior slope. This data will be monitored periodically by a member external to the Rizzoli Orthopaedic Institute.

8. Quality assurance

It is important to note that the medical device does not require a CE mark given that it is a customised product. ISO 9001:2014 and ISO 13485:2016 accreditations are to be obtained from BSI this year with the successful admission to phase 2 audits, following the completion of phase 1 on the 26th February. The phase 2 audit is planned on the 29th April to the 1st May, and certifications are scheduled to be received a few months after the 26th June. The study may be monitored, or audited in accordance with the current protocol, Good Clinical Practice (GCP), relevant regulations and standard operating procedures to ensure that quality standards are maintained.

Furthermore, to ensure that the device is being manufactured to a high-quality standard, data sheets for the titanium powder material, as well as the 3D printers used, are inserted in Appendices 17 and 18 respectively.

9. Auditing

Internal audits will be conducted periodically (every 3 months) to ensure that the investigation is being carried out according to protocol and that patient safety is achieved. Note that members of the Ethics Committee may also perform audits, if found necessary, to verify conformity and patient safety.

The audit must be performed by individuals who are qualified through training and/or experience and must undertake a fair and comprehensive audit of clinical investigation study files.

The auditors should allow 1-3 days for the conduct of a research audit and they must review all documentation provided, against known Governance approval documentation. Subsequently, they should record any findings or discrepancies on the Audit Checklist given in Appendix 19.

Audit findings may be classified into three groups and require the adoption of different measures, which can be seen below.

Category	Implication	Action required
Critical finding	Major breach of GCP, Declaration of Helsinki or protocol procedures without notification to Competent Authorities. Causes harm or increased immediate risk to study participants and/or affects the integrity of the study data.	Immediate cessation of all study activities until findings have been resolved.
Major finding	Breach of GCP, Declaration of Helsinki or protocol procedures without notification to Competent Authorities. Could cause harm to participant or integrity of study data if unresolved in a timely manner.	Findings are required to be investigated and resolved within 1 month. A follow-up visit may be arranged.
Minor or other finding	Low risk to participants but requires resolution before end of study.	Findings are required to be resolved by the next audit (3 months)

10. Deviation from protocol

Investigators must communicate/report deviations from protocols to the sponsor and Ethics Committee, especially if the deviation compromises patient safety.

11. Adverse events

An adverse event (AE) is defined as “any untoward medical occurrence in a clinical trial subject and which does not necessarily have a causal relationship with the treatment.”

A device related AE is defined as “an event that causes or has the potential to cause unexpected or unwanted effects involving the safety of device users (including patients) or other persons”

A serious adverse event (SAE) is “any untoward and unexpected medical occurrence” that:

- Results in death;
- Is life-threatening;
- Requires inpatient hospitalization or prolongation of existing hospitalization
- Results in persistent or significant disability/incapacity

Some AE and SAE are not unexpected in orthopaedic surgery and may not require reporting at all. Examples may include:

- Post-operative respiratory tract infections
- Urinary tract infections
- Dermatological events
- Pain in the contra-lateral knee
- Joint disease progressing in other joints and requiring treatment

Some AE and SAE are not unexpected in orthopaedic surgery and may require documenting without further reporting. Examples may include:

- Local knee issues such as discomfort, swelling, pain provided no more significant reason found for them
- Wound infection, deep vein thrombosis (DVT)

Other 'important medical events' may also be considered serious if they jeopardize the participant or require an intervention to prevent one of the above consequences. The Chief Investigator will advise on such matters.

Participants will be asked to inform their surgeon if any complications or adverse events occur and similarly request the surgeons to specifically ask their patients for this information at each clinic attendance.

A meeting of the research team will be held on a 3 monthly basis to discuss progress of the study, any specific problems and to consider whether there are any justifications for stopping the study. If adverse events that compromise patient safety occur the surgeon may decide to revert to the routine care procedures and replace the current implant with the standard device used for opening wedge HTOs in the Rizzoli. The identification of any unexpected complications that would require an early termination of the study are not anticipated, as HTO is a well-established procedure.

All serious and non-serious complications that relate to the investigation, including those occurring during the surgical procedure and throughout the post-operative evaluations, will be documented on the appropriate data forms with specific details of the symptoms, their severity, duration and outcome. All other serious adverse events which are fatal will also be recorded.

Any such events occurring in the immediate peri and post-operative events should be reported to the Chief Investigator by the surgeon in charge of the case who will contact the study sponsor. Similarly, if any such adverse events are identified in clinic, the surgeon concerned should report these events back to the Chief Investigator to be logged and the sponsor will be informed.

SAE's will be reported to the sponsor within 24hrs of the investigator being aware of the event. Any SAE occurring to a participant will be reported to the Ethics Committee that gives a favourable opinion of the study where, in the opinion of the Chief Investigator the event was 'related' (resulted from administration of any of the research procedures) and 'unexpected' in relation to those procedures. Reports of related and unexpected SAEs will be submitted within 15 working days of the Chief Investigator becoming aware of the event.

12. Protocol amendments

Following the positive opinion of the Ethics Committee, all the amendments that the sponsor or investigation team would like to make must be informed to the Ethics Committee. In particular substantial amendments require more scrutiny compared with the non-substantial amendments.

The chief investigator, with the collaboration of the research team is responsible for deciding whether an amendment is either substantial or non-substantial. This decision is based upon the significant impact an amendment may have on the following:

- The scientific validity of the study
- The management of the investigation
- The performance and safety of the medical device used
- The safety, physical or mental integrity of the patients enrolled
- Ethical aspects of the clinical investigation

It is important to note that not all amendments require authorisation by the Ethics Committee before being enforced. Such amendments that need only be transmitted for informative purposes must not have immediate or direct implications on the safety, ethics and scientific validity of the investigation. Once again, it is the responsibility of the chief investigator and the research team to determine the assignment of the amendments to each category.

13. Early interruption or suspension of study

The early interruption or suspension of the study can be initiated by either the Ethics Committee, the investigation team or the sponsor.

These can occur if there is the presence of reasonable doubts regarding the safety of the patients or the scientific research around the device in question.

However, if the investigating team or sponsor learns of new factors relating to the conduction of the investigation or the medical device that may influence the safety of the patients enrolled in the study, then it must implement measures to protect the individuals from any risks. These measures, which may include the early interruption or suspension of the study, and the problems that the measures intend to address, need to be informed to the Ethics Committee. It must also be noted that in the case of the suspension of the study, the investigation cannot be restarted until a notification of the substantial amendment is sent, followed by a positive opinion from the Ethics Committee. More information on protocol amendment can be found in Chapter 12.

If there is an early interruption or suspension of the study not related to safety considerations, the sponsor needs to justify the decision taken.

14. Confidentiality & conflicts of interest

The study staff will ensure that the participants' anonymity is maintained, and the participants will be identified only by participants ID number on all electronic databases. All documents will be stored securely and will only be accessible by study staff and authorised personnel. Furthermore, the study will comply with the General Data Protection Regulation (GDPR) requirements and the requirements displayed in the contract. All Rizzoli staff involved will be compliant with the code of confidentiality and will adhere to Good Clinical Practice principles.

The data associated with the study will be kept electronically on the hard drives of computers within the Rizzoli Orthopaedic Institute and within the 3D Metal Printing office (note that the data given to the sponsor will only have a patient ID and cannot trace back to the names of the individuals in the study). It will be stored on encrypted and password protected computers. The data will only be accessible by members of the clinical investigation team, along with members of staff who will require access to the data to ensure compliance with the protocol and conformity to all study regulatory requirements.

At the end of the study, all research data will be archived, and radiographs and scans will remain on secure systems.

Both members of the TOKA® design team and the clinical investigation team in the Rizzoli Orthopaedic Institute will complete the necessary applications regarding the clinical investigation to the ethics committee.

Furthermore, it must be noted that there are no conflicts of interest within this investigation.

15. Dissemination of results

Only the clinical investigation team at the Rizzoli Orthopaedic Institute, as well as the individuals involved in the study, who are employed by the manufacturer of the device, will be informed of the results. The participants will also be informed in writing of the results, by the clinical investigation team at the Rizzoli Orthopaedic Institute, if they so desire. Additionally, results may be published, but only patient identification numbers will be used to maintain anonymity.

The main investigator undertakes to produce the final report, publish all the data collected as described in the protocol and to ensure that the data is reported responsibly and consistently. In particular, the publication of the data deriving from this study will take place regardless of the results obtained. The transmission or dissemination of data, through scientific publications and / or presentations in congresses conferences and seminars, will take place exclusively following the merely statistical elaboration of the same, or in any case in an absolutely anonymous form.

16. Bibliography

Akizuki, S. et al. "The long-term outcome of high tibial osteotomy: a ten- to 20-year follow-up." *J Bone Joint Surg Br* 90.5 (2008): 592-6.

Bedson, J. and Croft, P. R. "The discordance between clinical and radiographic knee osteoarthritis: a systematic search and summary of the literature." *BMC musculoskeletal disorders* 76.6 (2008): 887-92.

Elson, D. W et al. "High reliability in digital planning of medial opening wedge high tibial osteotomy, using Miniaci's method." *Knee Surgery, Sports Traumatology, Arthroscopy* (2015): 2041-2048.

Han, J. H. et al. "Is Bone Grafting Necessary in Opening Wedge High Tibial Osteotomy? A Meta-Analysis of Radiological Outcomes." *Knee Surgery & Related Research* (2015): 207-220.

Harris, J. D. et al. "Survival and clinical outcome of isolated high tibial osteotomy and combined biological knee reconstruction." *Knee* 20.3 (2013): 154-61.

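### Section 11 defines a serious adverse event as unexpected, then lists expected ones that may go unreported, and does not tie those lists to the 24-hour sponsor rule

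*Protocol*

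**What the plan says.** All of the relevant text is in Section 11 (Adverse events) of the protocol.

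- **Definition.** An SAE is "any untoward and unexpected medical occurrence" that meets one of four criteria: death, threat to life, hospital admission or a longer stay, or lasting or significant disability.
- **First list.** "Some AE and SAE are not unexpected in orthopaedic surgery and may not require reporting at all". The examples include respiratory and urinary tract infections, skin events and pain in the opposite knee.
- **Second list.** "Some AE and SAE are not unexpected in orthopaedic surgery and may require documenting without further reporting". The examples are local knee problems, provided no more significant cause is found, and wound infection and DVT.
- **Other important medical events.** These "may also be considered serious if they jeopardize the participant or require an intervention to prevent one of the above consequences", and the Chief Investigator advises on them.
- **Documentation.** "All serious and non-serious complications that relate to the investigation" are documented on the data forms. Beyond these, only fatal SAEs are added.
- **Route to the sponsor.** Such events around and after surgery "should be reported to the Chief Investigator by the surgeon in charge of the case who will contact the study sponsor". For those found in clinic, "the surgeon concerned should report these events back to the Chief Investigator to be logged and the sponsor will be informed".
- **Deadlines.** SAEs go to the sponsor within 24 hours of the investigator becoming aware. SAEs judged both related and unexpected go to the Ethics Committee within 15 working days.

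**The concern.** Under the definition, an SAE that is not unexpected cannot exist, yet the section twice describes such events and gives them lighter handling. The 24-hour rule refers to neither list, and neither list says whose report is waived: the sponsor's, the Chief Investigator's or the Ethics Committee's.

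This matters more than a loose phrase usually would. Section 7 says the device has had no clinical experience. Section 4 gives infection as an example of its risks, while wound infection sits on the document-only list. Read literally, the definition takes a foreseeable serious infection out of the only sponsor report that has a deadline. Section 13 gives the sponsor, alongside the investigating team, a duty to act on new safety information once it is learned, so the time at which the sponsor hears of an event has a stated use. Section 9 provides for audits against the protocol, and an auditor could not tell from this text whether an unreported serious DVT was a deviation.

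**Working it through.** No formula applies and the protocol gives no event rate, so the check is to follow example events through the text.

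**Step 1: a DVT that prolongs the hospital stay.** It meets a seriousness criterion and is named on the second list as not unexpected.

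| Text followed | Is it an SAE? | Report to sponsor |
|---|---|---|
| Definition, read literally | No, because it is foreseeable | Not under the 24-hour rule |
| Second list | Yes, but expected | Document only, at discretion |
| 24-hour rule, with seriousness alone making the SAE | Yes | Within 24 hours |

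One event gets three answers.

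**Step 2: which use of the term is the outlier?** Both lists assume that an SAE can be expected. The Ethics Committee rule applies unexpectedness as a further test on SAEs, which would add little if every SAE were already unexpected. Only the definition builds expectedness in.

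**Step 3: how events reach the sponsor.** Three sentences carry them:

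1. events around and after surgery, through the Chief Investigator: no time limit;
2. events found in clinic, through the Chief Investigator: no time limit;
3. SAEs: 24 hours.

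So 1 of 3 has a deadline, and it covers only events labelled SAE.

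**Step 4: what changes when the label is lost.**

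- *Related to the investigation:* sentences 1 and 2 still apply, with no exception for listed events. The event is documented and passed on, but a 24-hour deadline becomes no stated deadline.
- *Judged unrelated, listed and non-fatal* (for example, a respiratory infection needing admission): the documentation sentence does not reach it, since beyond related complications it adds only fatal SAEs. A 24-hour deadline becomes discretion.

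**Step 5: does other wording settle it?** The proviso on local knee problems covers only that bullet. The Chief Investigator's advisory role is attached to other important medical events, not to a listed event that already meets a seriousness criterion. Neither resolves the conflict.

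**The case against.** The best reply is that the word in the definition is a drafting slip. Every operative use in the section keeps expectedness apart from seriousness, the lists are permissive and the 24-hour rule is unconditional, so a site that reports every serious event within 24 hours breaches nothing. That is correct, but it concedes that the definition is wrong. It also leaves a site free to follow the definition or the lists instead.

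A second reply is that the lists waive only onward reporting to the Ethics Committee, since their wording mirrors that filter. This suits the second list fairly well. The protocol does not say it, however, and the first list's waiver of any reporting whatever reads against it. The definition would still need correcting.

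Third, there are safeguards. Surgeons are to ask about events at each clinic attendance, the research team meets every 3 months to consider whether the study should stop, and internal audits run every 3 months. These limit the risk that events are missed, and no missed events are claimed here. They do not supply the deadline.

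Fourth, the link to Section 13 is thin. Knowledge held by either the investigating team or the sponsor triggers the duty, the team will usually know first, and a foreseeable infection is not obviously new information. This stands as a limit on the consequence. The sponsor is still named as a party with that duty.

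Finally, the case report form and risk management documents are listed as appendices but not shown. They may hold reporting instructions, but they would not remove a contradiction within Section 11.

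**Conclusion.** The concern holds. The SAE definition contradicts its own use in the same section, and the relation between the two lists and the 24-hour rule is undefined. This is a rule stated wrongly, not detail left for a later document.

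The effect is bounded. For related events, the doubt is over SAE classification and timing: 24 hours against no stated limit. For listed, non-fatal events judged unrelated, it is over whether they are reported at all. The count of one deadline in three sentences describes the text and does not measure harm. With no event rate in the protocol, no rate of delay or under-reporting can be derived, and the imaging outcomes in Section 8.3 are untouched. The conclusion rests on the wording of Section 11 alone. It should be corrected because the device is new to patients and the correction is small.

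**What to change.** Reconcile Section 11 with two changes.

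1. Remove expectedness from the SAE definition, so that seriousness alone makes an SAE. Keep expectedness where it already works, as the Ethics Committee filter. That filter is already defined against the research procedures and can stay as it is.
2. State that the two lists do not exempt an event meeting a seriousness criterion from the 24-hour sponsor report. If an exemption is intended, write it into the 24-hour rule itself and say which events and which recipient it covers.

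The cost is two wording changes in one section, notified to the Ethics Committee under Section 12, where the chief investigator and research team decide whether the amendment is substantial. The downside is slightly more event paperwork for 25 patients.
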